Will “negative results... guide further intervention development”? This R33 has clear ‘Go/No-Go’ criteria. **If target engagement is not confirmed**, we will conclude that this design setting is unsuitable for detecting robust AMPH group effects on APS learning. Based on the data (e.g. evidence of AMPH bioactivity), we will develop testable hypotheses (e.g. cohort differences) that might account for differential outcomes in the present application vs. studies in MH59803. Even if there are not robust AMPH effects on APS learning (target engagement), it is possible that heterogeneity in AMPH APS sensitivity might reflect meaningful subgroups of patients (e.g. low vs. high attention/vigilance), and that APS AMPH sensitivity might still predict (correlate with) AMPH enhancement of TCT therapeutic effects. In other words, a lack of a group difference (placebo vs. AMPH) would not preclude the utility of AMPH APS sensitivity as a predictive biomarker. Conversely, even if target engagement is confirmed, it is possible that group differences (placebo vs. AMPH) in therapeutic gains might not be detected. A “valid” negative outcome (e.g. lack of positive AMPH effects on outcome measures despite evidence of target engagement and adequate TCT exposure) will indicate that AMPH-enhanced APS learning is not sufficient to enhance TCT effects in a clinically-defined SZ cohort. Analyses will then determine if AMPH enhances TCT effects in biomarker-defined SZ subgroups. A failure to detect such subgroups would suggest a dissociation between target engagement in the first Sound Sweeps session and therapeutic benefit after 30-h of TCT. Factors contributing to this dissociation might include (among other possibilities): 1. Tolerance to the “pro-learning” properties of AMPH (unexpected, since AMPH retains pro-attentional effects, even after years of daily use); 2. State-dependent learning (discussed above); 3. Adverse effects of AMPH on psychosis, akathisia or other symptoms; such effects will be assessed via clinical metrics (below). Analyses of these and other factors that might impede AMPH-induced gains will guide further development of both TCT and PACT interventions.

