**Aim 2 – Test clinical, neurocognitive and functional impact of AMPH on TCT, and its relationship to target engagement:** We will determine if AMPH+TCT produces greater, faster or more durable clinical, neurocognitive or functional gains from baseline, compared to PBO+TCT, over a 30-session course of TCT. A Cohen’s  $d \geq 0.5$  for the main effect of drug (PBO vs. AMPH) or drug x session (#10, 20, 30) interaction in an LME model is the primary “Go” criteria. The main effect of drug assesses “greater” gains. Reverse Helmert contrasts for session assesses “faster” gains. A separate model comparing differences in outcomes at 12-weeks post-TCT assesses “more durable” gains. Secondary regression analyses will examine whether change in AMPH-enhanced APS learning (“within-subject” target engagement; Aim 1) predicts gains in Aim 2 outcome measures.

**Aim 3 – Biomarkers of AMPH-induced gains:** We will determine if baseline levels of specific neurocognitive or EEG-based measures, or changes in specific measures with initial AMPH exposure (Test 2 vs. 1), predict greater sensitivity to AMPH-enhanced neurocognitive, clinical or functional gains over 30-h of TCT. Regression analyses will assess whether specific candidate biomarkers predict AMPH-enhanced gains in outcome measures.

**Subject “throughput”:** We will enroll and screen 23 subjects/yr, test target engagement in 18 subjects/yr, and (conservatively) complete TCT training in 12 subjects/yr. This will yield 2 “target engagement” Aim 1 arms of  $n=27$ , and (conservatively) 2 TCT completion Aim 2 arms of  $n=18$ . Training capacity (2 TCT stations with morning and afternoon sessions on M, W and F, with T and Th “make-up” days for missed appointments, 48 weeks/year) allows for a “maximum throughput” of 19.2 subjects/yr. To reach the target of **12 TCT-completing subjects /year**, we would need to maintain training rates of **62.5% capacity**. This is well within our historical testing levels.

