General Statistical Approach: Hypothesis tests are 2-sided ($\alpha=.05$). Type I error is controlled by selecting optimal *a priori* targets for primary analyses; secondary analyses use false discovery rate corrections. When appropriate, missing data are handled via multiple imputation or full information maximum likelihood estimation. Expected drop-out rates and ways to minimize them are described in the parent application.

Differential drop-out rates from PBO vs. AMPH arms are monitored. Clinical follow-up is pursued with all patients exiting the study through post-TCT week 12.

Cohort differences: For between-subject contrasts (drug), baseline demographic, clinical, antipsychotic/anticholinergic load and performance differences are tested and used as covariates if indicated. Sex differences are tested for all measures.

Procedures for Alternative or Unexpected Results: Linear mixed-effects models allow for the analysis of all available data using an intent-to-treat approach. This approach, however, assumes that data are missing at random. A potential concern is nonrandom dropout, particularly when dropout is related to the (missing) outcomes; that is, not missing at random. To make the missing at random assumption more plausible, we will explore the use of auxiliary variables. Auxiliary variables are covariates that predict both dropout and outcomes. By adding auxiliary variables to our models, nonrandom dropout is corrected by conditioning treatment effects on the predictors of dropout.

Primary Efficacy Endpoint(s): Aim 1: Target engagement – APS learning will be significantly greater under AMPH vs. PBO conditions. Aim 2: Pilot trial - Compared to PBO arm patients, AMPH arm patients will exhibit greater clinical benefit, as indicated by one or more of the following: greater, faster or more durable improvements in PANSSt (reduced scores; see below, “Go/No-Go”), MCCBc (increased scores) or WHODAS (reduced scores).

Secondary Efficacy Endpoint(s): Aim 3: Biomarkers - baseline levels of specific neurocognitive or EEG-based measures, or changes in specific measures with initial AMPH exposure, predict greater sensitivity to AMPH-enhanced neurocognitive, clinical or functional gains over 30 sessions of TCT.

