Comparable analytic approaches will be used for neurocognition (MCCBc) and function (WHODAS) as described in "Research Strategy". Data will be described as means with SEM. Tests for normalcy will be applied to all data and non-parametric comparisons will be used if normalcy is not demonstrated. The Analysis Set for these data will be all subjects who have completed 30h of TCT and post-TCT clinical, neurocognitive and function assessments. When appropriate, missing data are handled via multiple imputation or full information maximum likelihood estimation.

Secondary regression analyses assess the predictive value of putative biomarkers on clinical, neurocognitive or functional gains from the addition of AMPH to TCT. Future studies with larger samples will assess potentially more informative models, e.g. Path Analysis to study moderating effects of APS AMPH sensitivity and biomarkers on both indirect (moderated-mediation) and direct paths between treatment and outcome.

Power analyses

Consistent with the FOA, this study will adequately power tests of target engagement (Aim 1) for traditional significance, while the "Go" signal for therapeutic impact (Aim 2) is based on effect size ($d=0.5$). To detect target engagement with $d=0.5$, 80% power, $\alpha=0.05$, test-retest correlation =0.8, and a linear treatment effect, $n=27$ randomized participants are required per group. This is a very conservative estimate of d for target engagement, since empirically, d for target engagement with 5 mg amphetamine was 0.85 (Fig. 3A). A future Confirmatory Efficacy trial will be powered to apply more robust approaches to Aim 2, e.g. Path Analysis¹⁰⁸ to study moderating effects of APS AMPH sensitivity and biomarkers on both indirect (moderated-mediation) and direct paths between treatment and outcome.

Project Modification: Statistical Analysis Plan

The original study design included separate, parallel assessments of amphetamine (AMPH) (vs. placebo (PBO)) and memantine (MEM) (vs. PBO) effects on TCT-associated clinical, neurocognitive and functional gains. However, these designs pre-dated the pandemic, and between the date that they were proposed (10/2019) and the project start date (8/2020), our institution implemented a pandemic-related shut-down of clinical research activities. Even with the gradual resumption of research activities, recruitment lagged significantly behind target levels. As a result, we made several pragmatic adjustments to the original study designs:

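### A negative Aim 2 result is to be read as showing the mechanism insufficient, with no precision condition, although 18 completers per arm can seldom exclude the plan's own meaningful d of 0.5

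*Protocol*

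**What the plan says.** The Protocol's Research Strategy has a paragraph on what negative results would mean. It describes a valid negative Aim 2 outcome as a "lack of positive AMPH effects on outcome measures despite evidence of target engagement and adequate TCT exposure" and says that this outcome "will indicate that AMPH-enhanced APS learning is not sufficient to enhance TCT effects in a clinically-defined SZ cohort". Biomarker-defined subgroups are then examined. Finding none "would suggest a dissociation between target engagement in the first Sound Sweeps session and therapeutic benefit after 30-h of TCT", and the paragraph lists tolerance, state-dependent learning and adverse effects among the possible reasons. Chance and imprecision are not listed, although the list is left open.

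The Go threshold for Aim 2 is an observed d of 0.5, which the Protocol treats as clinically meaningful (Outcome and Go Decisions). Limitation #6 concedes that the sample will not easily give significant group differences. Subject throughput plans for "2 TCT completion Aim 2 arms of" 18, and the Recruitment and Retention Plan repeats that number. Neither document specifies a confidence interval for d; the SAP describes data by means and SEM.

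**The concern.** Failing to reach a threshold on a point estimate is not the same as showing that the effect is smaller than the threshold. The paragraph moves from one to the other by checking engagement and exposure, but not whether the estimate is precise enough to rule out an effect worth having. The Protocol promises a result of scientific use whether positive or negative. If an imprecise estimate is reported as evidence that enhanced learning does not enhance TCT, a reader planning the confirmatory trial is told more than the data can show. The subgroup step adds to this, because it draws a further conclusion from a non-finding in smaller groups.

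**Working it through.** **Inputs.** 18 completers per arm (Subject throughput; Recruitment and Retention Plan); 27 randomised per arm; meaningful d = 0.5; three primaries (PANSS total, MCCB composite, WHODAS), any one of which can give a Go. Assumed, because the documents do not give them: correlations of 0 to 0.5 between primaries, 0.7 between looks, and normal outcomes.

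**The plan's own figure.** The power statement reads "To detect target engagement with $d=0.5$, 80% power, $\alpha=0.05$, test-retest correlation =0.8, and a linear treatment effect". On change scores the SD is sqrt(2(1 − 0.8)) = 0.632 raw SDs. A two-sided t test then has 79.8% power at 26 per arm and 81.3% at 27, so the stated 27 per group reproduces. That calculation covers Aim 1 only; Aim 2 has none.

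**Width of the Aim 2 interval.** Half-width ≈ 1.96 × s × sqrt(2/n), where s is the SD of the analysed score in the units of d.

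| n per arm | Scale of d | Half-width | Upper limit if observed d = 0.2 | Observed d needed to exclude 0.5 |
|---|---|---|---|---|
| 18 | SD of analysed score (s = 1) | 0.65 | 0.85 | below −0.15 |
| 27 | SD of analysed score (s = 1) | 0.53 | 0.73 | below −0.03 |
| 18 | raw SD, r = 0.8 (s = 0.632) | 0.41 | 0.61 | below 0.09 |

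The scale matters and is not fixed. The Protocol takes d from a mixed model through an R package. The SAP's Project Modification divides by a weighted average SD without saying of which score. The 0.8 is stated for Aim 1; using it for Aim 2 outcomes is an assumption. An observed d of zero fails to exclude 0.5 in the first two rows but does exclude it in the third.

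**How often a useful drug misses the threshold.** At 18 per arm and true d = 0.5, the noncentral t gives P(observed d ≥ 0.5) = 0.504 for one measure, so the miss rate is 0.496. At true d = 0, P(observed d < 0.5) = 1 − 0.071 = 0.929. With independent outcomes and one look, the chance that all three miss is:
- one primary benefits: 0.496 × 0.929² = 0.43;
- two benefit: 0.496² × 0.929 = 0.23;
- all three benefit: 0.496³ = 0.12.

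Simulation with correlations from 0 to 0.5 gives 42-48%, 23-32% and 12-25%. Counting two looks gives 29-35%, 12-20% and 5-14%. These last figures may be too low, because the faster route in Fig. 8 also needs a significant interaction. If the SAP's significance wording for PANSS total governs instead, one measure with true d = 0.5 is missed 69% of the time at 18 per arm (power 0.308).

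**Subgroups.** As an illustration, an even split leaves 9 per arm: 1.96 × sqrt(2/9) = 0.92. Failure to see an effect there says little.

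**The case against.** **The sample is openly a pilot.** Limitation #6 and the Go section disclose the limited size, and an effect-size threshold is a reasonable Go rule. That stands, and the rule needs no change. But disclosing low power does not turn an estimate below 0.5 into evidence of insufficiency.

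**The trigger may be narrower than missing 0.5.** A lack of positive effects could mean observed d at or below zero on all three primaries. With true d = 0.5 on all three, that happens in under 1% of trials. With one benefiting and independent outcomes it is about 0.067 × 0.5 × 0.5 = 2%. This is a fair point: how often a wrong conclusion follows depends on a trigger that the Protocol does not define. The interval argument does not depend on it in the same way, since on the first two scalings an observed zero still leaves 0.5 inside the interval.

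**The 50% per-measure miss is not a sample-size effect.** Correct. It arises because the threshold equals the assumed effect, and it is the same at 27 per arm. The sample-size argument is the interval width.

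**The wording is qualified.** The claim covers an unselected cohort with engagement shown, and the dissociation sentence is hedged. The hedge makes that sentence milder; the main Aim 2 sentence remains categorical.

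**A stronger reading that does not hold.** A reader might infer that Aim 1 has the same fault, because the Protocol says of a negative Aim 1 that "we will conclude that this design setting is unsuitable for detecting robust AMPH group effects on APS learning". The documents do not support this. Aim 1 has 27 per arm, not 18. Data Analysis, Aim 1, accepts either the within-subject or the between-arm contrast. At d = 0.5 and r = 0.8 the powers are about 98% and 81%, and about 98% for either, so a miss occurs in about 2% of trials. The sentence is also limited to robust group effects, and the text keeps open the use of APS sensitivity as a predictor.

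**Conclusion.** The point holds for Aim 2 only. The categorical conclusion of insufficiency has no precision condition, and at the planned size most results below the threshold remain compatible with d = 0.5: those above about −0.15 on the wider scaling at 18 per arm, and those above about 0.09 on the narrower one. A useful drug giving no Go at a single look is common if it helps one domain (42-48%), less so for two (23-32%), and a minority outcome if it helps all three (12-25%); the other routes to Go lower each figure. It would therefore be too strong to say that a drug effective in every domain often fails. The Protocol itself expects that gains may appear in some metrics and not others, so the one- and two-domain cases are relevant. The rates rest on the assumed correlations and on reading a negative as no primary reaching 0.5. The SAP's Project Modification reports samples well below target and a 2:1 allocation; smaller samples widen the intervals, but the document gives no numbers from which to compute by how much.

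**What to change.** For Aim 2, report the 95% interval for the AMPH-PBO d on each primary, and state which SD standardises it. State insufficiency for an outcome only where the upper limit is below 0.5; otherwise report that outcome as inconclusive. Do not read failure to find a responsive subgroup as evidence that engagement and benefit are dissociated. Leave the Go rule and the Aim 1 wording as they are.

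The cost is a change of wording and intervals from models already planned. The real downside is that firm negatives become uncommon. If the drug truly has no effect, then at 18 per arm on the wider interval a single outcome excludes 0.5 in about 32% of trials (observed d below −0.153, SE 0.333), and all three do so in roughly 3-11% (correlations 0-0.5). On the raw-SD scaling a single outcome does so in about 66% (below 0.087, SE 0.211). The report should say plainly that a trial of this size can seldom establish insufficiency.

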**Fig. 8. “Go” criteria: #1, plus at least one of #’s 2, 3 & 4 ( $d > 0.5$ )**

1. **Target engagement:** APS learning, AMPH > PBO,  $p < 0.05$
2. **Greater clinical, neurocognitive or functional gains:**
  - $\downarrow$ PANSSt,  $\uparrow$ MCCB-C or  $\uparrow$ Fnxn: AMPH+TCT > PBO+TCT
3. **Faster clinical, neurocognitive or functional gains:**
  - drug group x session interaction ( $p < 0.05$ ) followed by AMPH+TCT > PBO+TCT at specific session # or combination;
4. **More durable** clinical, neurocognitive or functional gains:
  - AMPH+TCT > PBO+TCT at post-TCT week 12.

PANSSt: Positive & Negative Symptom Scale total; MCCB-C: MATRICS Composite; Fnxn: Function (assessed via the World Health Organization Disability Schedule 2.0 (WHODAS))

**Outcome and “Go Decisions”.** In addition to confirming “target engagement”, this application tests the hypothesis that SZ patients given AMPH +TCT will exhibit greater, faster and/or more durable improvements (change from baseline) in symptoms, neurocognition and/or function compared to patients given PBO+TCT, and that this enhanced clinical response will be associated with greater AMPH-enhanced TCT learning.

The small “n” necessitated by the 3-year timeline and demanding treatment schedule greatly constrains the total number of outcome measures.

Moreover, the plan to assess not only magnitude but also rate and durability of PACT gains triples the number of primary analyses. Thus, we selected only one **primary** clinical, neurocognitive and functional outcome measure (Fig. 8) – recognizing that they are relatively “blunt” metrics - but will track several other, more focused, measures as well as inter-measure correlations in exploratory analyses to inform future studies.

A “Go” decision requires: 1) confirmation of target engagement (APS learning, AMPH>PBO,  $p < 0.05$ ); 2) evidence of gains from PACT ( $d \geq 0.5$  (AMPH > PBO)) in primary clinical, neurocognitive and/or functional measures (Fig. 8), and 3) the absence of adverse effects of AMPH that are significantly greater than PBO levels. The decision to not use traditional statistical significance as “Go” criteria for Aim 2 reflects this RFA’s call for “Pilot” studies, the need to identify candidate treatments for a subsequent larger “n” Confirmatory Efficacy R01 study, and the limits in sample size resulting from the 3-year R33 duration. Cohen defined a medium effect size ( $d=0.5$ ) as one that is “visible to the naked eye,” and this amount of change is viewed as clinically meaningful in trials targeting negative symptoms. This  $d=0.5$  “Go” threshold for Aim 2 corresponds to a “number needed to treat” (NNT) value  $\approx 3.62$ . While a “Go” decision does not require identification of a biomarker predicting greater PACT

sensitivity (Aim 3), the identification of one or more meaningful predictors that could be incorporated into a Confirmatory Efficacy trial would favorably impact a “Go” decision.

Staff assessing outcome measures are blind to treatment arm, and for some measures receive training using videotaped and practice interviews until achieving high (ICC>.80) reliability based on 20 assessments by 2 raters. We achieve high inter-rater reliability (e.g., ICC>0.85 for PANSS total), and check for rater drift each 90d.

**Specific Procedures: TCT** is completed with a dedicated room and equipment. Staff trained with a UCSD-developed “TCT Clinician Competence Assessment” monitor TCT, clarify instructions and provide encouragement as needed. In the initial “biomarker testing” session (Test 1), all subjects receive a PBO pill and complete 1-h of Sound Sweeps to generate a “PBO APS score” as described previously (Fig. 2A,B). Treatment group assignment (PBO vs. AMPH) is then made using stratified random sampling (above), and 5-7 days later patients ingest either PBO (n=27) or 5 mg AMPH (n=27) 60 min before completing the Sound Sweeps session (“Test 2”). AMPH effects on APS learning are assessed both within-subject (APS (Test 1 - Test 2) for AMPH group subjects: a key measure of AMPH sensitivity) and between subjects (APS Test 2, PBO vs. AMPH groups). For all other sessions, subjects receive either PBO or AMPH 60 min before TCT, which includes 5 modules of auditory/verbal processing exercises. Each module increases in difficulty as performance improves: 1) Sound Sweeps; 2) Syllable Identification: Patients distinguish between 2 similar phonemes (e.g., “ba” vs. “da”), differing only in their voice onset time; 3) Word Matching: Subjects match short similar-sounding consonant-vowel-consonant words (e.g., bad, dad); 4) Listen & Do: Subjects reconstruct a spoken series of instructions and use a computer mouse to click icons on the screen in a specified order. This exercise is designed to stimulate verbal WM processes supported by the lateral PFC as well as premotor and motor processes. 5) Rhythm Recall: Subjects listen to and replicate a short rhythmic sequence. This task is designed to stimulate both basic auditory processes supported by primary auditory cortex, and non-verbal auditory WM.

**Symptoms** are assessed (Fig. 4B) to track clinical status, and TCT response. TCT reduces both positive and negative symptoms of psychosis, and we predict that AMPH will augment these effects via enhanced TCT learning (i.e. not via a lasting direct pharmacological effect of AMPH), detected by the Positive & Negative Syndrome Scale. For this reason, and based on the need to limit total outcome measures, PANSS Total Score is the primary clinical outcome measure. Positive and negative symptom subscales, as well as PANSS factor-derived measures, will be assessed in exploratory analyses. Other secondary clinical measures will include: 1) Psychotic Symptom Rating Scales (PSRS; assesses auditory hallucinations); 2) Young Mania Rating Scale; 3) Patient Health Questionnaire-9 (PHQ-9; current depressive symptoms); 4) Abnormal Involuntary Movement Scale (AIMS); 5) C-SSRS; “Lifetime/Recent version” at screen; “Since Last Visit” at follow-up visits). The C-SSRS is a reliable, valid and sensitive measure of suicidal ideation; any “yes” in C-SSRS prompts an immediate full evaluation/action plan by a study M.D.; and 7) AMPH Cessation Symptom Assessment (ACSA).

**Neurocognition:** Change in MCCB Composite performance from baseline is one outcome measure. The MCCB measures 7 cognitive domains: SP, A/V, WM (verbal and nonverbal), verbal learning, visual learning, reasoning/problem solving and social cognition. Details are found in; past studies by the PI of drug effects on MCCB performance include. Since the MCCB is assessed multiple times, alternate forms of the HVLT-R and BVMT-R are used in counterbalanced order. MCCB Global Composite T-score (MCCB-C) is the primary neurocognitive outcome measure. Individual MCCB domain T-scores are used in secondary analyses to determine whether an overall effect is driven by specific aspects of neurocognition; TCT effects on verbal learning performance are known to be robust, and should be augmented by AMPH. Baseline and AMPH-enhanced (Test 2 vs. 1) MCCB performance (A/V subscale) will also be tested as potential biomarkers/moderators of AMPH PACT efficacy.

**Function** is assessed via the World Health Organization Disability Schedule 2.0 (WHODAS) at baseline, after sessions 10, 20 and 30, and week 12 post-TCT. WHODAS 2.0 is a 12-item patient-rated measure (< 15 min) using a 5-point Likert scale focusing on cognition, mobility, self-care, getting along with people, life activities and participating in society; it was recommended by the DSM-5 Task Force committee to replace the global assessment of functioning scale. NIH “PhenX Toolkit” scales of Impairment, QOL and Social Isolation will also be used. After session #30, the assessment will include a 14-item 7-point Likert scale of treatment satisfaction.

**Biomarkers** from Tests 1-2 will be assessed as predictors of target engagement (Aim 1) and PACT sensitivity (Aim 2); in some cases, these measures will also inform mechanistic models for PACT: 1. AMPH-enhanced APS learning is both an outcome measure (Aim 1, “target engagement”) and candidate predictor of clinical outcome (Aim 2); 2. Baseline and AMPH-enhanced MCCB A/V scores are associated with APS AMPH sensitivity, and thus may predict clinical outcome (Aim 2); 3. ERP measures of early auditory information processing variably predict response to early APS learning, AMPH-enhanced APS learning, and TCT outcomes. EEG/ERPs are acquired via 64-channel recording systems and assessed in the same order, as per: MMN/P3a/Theta power/Phase locking (25 min; Oddball Paradigm), ASSR (6 min). 4. Auditory discrimination: Words-In-Noise (WIN; NIH Toolbox) and Speech-In-Noise (Quick-SIN; Etymotic Research) are acquired at Tests 1-2, TCT hour 30 and week 22. Both measures assess the ability to recognize speech over background noise, mimicking a

conversation in a noisy environment, and are thought to index peripheral (WIN) vs. more central (QuickSIN) auditory processing. AMPH-enhanced auditory discrimination (Test 2 vs. 1) may predict PACT outcome (Aim 2); gains in auditory discrimination over 30 hours of TCT, and their augmentation by AMPH, will be tracked to inform evolving models of PACT mechanisms (e.g. Figs. 1 & 6). **Predictions:** First and foremost, target engagement (AMPH-enhanced APS learning) will predict AMPH-enhanced TCT outcomes (Aim 2) as described below. Exploratory analyses will test secondary predictions: for example, high vs. low baseline P3a amplitude and faster P3a latency will predict greater target engagement (Aim 1), and greater AMPH-enhanced TCT outcome (Aim 2). AMPH-enhanced (Test 2 vs. 1) ERPs, auditory discrimination and neurocognitive (A/V) measures will also be explored as outcome (Aim 2) predictors; significant pre- vs. post-TCT changes in ERP source dynamics will also be examined for mechanistic characterization. Robust biomarker predictors will be examined as moderators of both indirect and direct paths between treatment and outcome in a future Confirmatory Efficacy trial.

**Data Analysis:** “Go/No Go” decisions are based on traditional statistical significance (Aim 1) and effect sizes (Aim 2). Formal statistical testing is conducted using linear mixed-effects (LME) models; hypothesis tests are 2-sided ( $\alpha=0.05$ ). Model parameters are estimated via the R lme4 package and Cohen’s  $d$  is estimated via the EMAtools package. Type I errors are minimized by constraining the number of primary analyses; secondary analyses use false discovery rate corrections. Expected attrition rates are described above. Because outcome measures involve a “change from baseline”, baseline metrics are compared between PBO and AMPH arms, and any baseline differences are addressed in the outcome analyses. Differential drop-out rates from PBO vs. AMPH arms are monitored. Data are assumed to be missing at random; full information maximum likelihood estimators are used, and all data/cases are included in analyses. Clinical follow-up is pursued with all patients exiting the study through post-TCT week 12. Cohort differences: For between-subject contrasts (main effect of drug), differences in age, antipsychotic and anticholinergic loads are tested and used as covariates. Sex differences are tested for all measures based on known sex differences in AMPH sensitivity. NIH Data Harmonization: 3 “PhenX Toolkit” (NOT-MH-15-009) measures of function are used; see above and “Resource Sharing Plan”.

**Aim 1 – Confirm target engagement:** The primary dependent measure of target engagement is AMPH-enhanced APS learning. APS learning is defined as the reduction in Sound Sweeps APS threshold (ms) pre- to post-assessment. Target engagement was demonstrated in MH59803, and will be confirmed if APS learning is increased by AMPH either in a within-subject comparison (AMPH group, “Test 2 vs. 1”), or in a between-subject comparison (AMPH group vs. placebo group change “Test 2” vs. “Test 1”) (note that AMPH and PBO groups are matched by Test 1 PBO performance via stratified randomized assignment). Effect sizes and inferential statistics are based on LME models with random intercepts. A statistically significant main effect of drug (PBO vs. AMPH) on APS learning in either within- or between-subject contrasts is a “Go” criteria and confirms target engagement.

**Aim 2 – Test clinical, neurocognitive and functional impact of AMPH on TCT, and its relationship to target engagement:** We will determine if AMPH+TCT produces greater, faster or more durable clinical, neurocognitive or functional gains from baseline, compared to PBO+TCT, over a 30-session course of TCT. A Cohen’s  $d \geq 0.5$  for the main effect of drug (PBO vs. AMPH) or drug x session (#10, 20, 30) interaction in an LME model is the primary “Go” criteria. The main effect of drug assesses “greater” gains. Reverse Helmert contrasts for session assesses “faster” gains. A separate model comparing differences in outcomes at 12-weeks post-TCT assesses “more durable” gains. Secondary regression analyses will examine whether change in AMPH-enhanced APS learning (“within-subject” target engagement; Aim 1) predicts gains in Aim 2 outcome measures.

**Aim 3 – Biomarkers of AMPH-induced gains:** We will determine if baseline levels of specific neurocognitive or EEG-based measures, or changes in specific measures with initial AMPH exposure (Test 2 vs. 1), predict greater sensitivity to AMPH-enhanced neurocognitive, clinical or functional gains over 30-h of TCT. Regression analyses will assess whether specific candidate biomarkers predict AMPH-enhanced gains in outcome measures.

**Subject “throughput”:** We will enroll and screen 23 subjects/yr, test target engagement in 18 subjects/yr, and (conservatively) complete TCT training in 12 subjects/yr. This will yield 2 “target engagement” Aim 1 arms of  $n=27$ , and (conservatively) 2 TCT completion Aim 2 arms of  $n=18$ . Training capacity (2 TCT stations with morning and afternoon sessions on M, W and F, with T and Th “make-up” days for missed appointments, 48 weeks/year) allows for a “maximum throughput” of 19.2 subjects/yr. To reach the target of **12 TCT-completing subjects /year**, we would need to maintain training rates of **62.5% capacity**. This is well within our historical testing levels.

**Power analyses:** Consistent with the FOA, this study will adequately power tests of target engagement (Aim 1) for traditional significance, while the “Go” signal for therapeutic impact (Aim 2) is based on effect size ( $d=0.5$ ). To detect target engagement with  $d=0.5$ , 80% power,  $\alpha=0.05$ , test-retest correlation =0.8, and a linear treatment effect,  $n=27$  randomized participants are required per group. This is a very conservative estimate of  $d$  for target engagement, since empirically,  $d$  for target engagement with 5 mg amphetamine was 0.85 (Fig. 3A). A future Confirmatory Efficacy trial will be powered to apply more robust approaches to Aim 2, e.g. Path Analysis to study moderating effects of APS AMPH sensitivity and biomarkers on both indirect (moderated-mediation) and direct paths between treatment and outcome.

